
Criteria for Evaluation
	
Safety: to be assessed through the analysis of routine laboratory tests (haematology, serum chemistry, urinalysis), physical examinations, vital signs, and ECOG status. Adverse event monitoring will be performed and assessed using the CTCAE National Cancer Institute Common Terminology Criteria for Adverse Events, Version 4.03 (CTCAE) scoring system.
 
Efficacy: All efficacy assessments will be performed at the discretion of the Investigator but at a minimum should include a baseline assessment (CT scan, ECOG assessment) and follow-up assessments at a minimum of every 12 weeks while receiving study drug. Tumor response and progression-free survival will be assessed using standard RECIST criteria.
 
Pharmacokinetics: blood and 24 hour-urine samples will be analysed to determine the primary idronoxil metabolites and the primary route of excretion.
 
Biomarkers: Ceramide and sphingosine-1-phosphate (related to the molecular target of idronoxil) and ENOX2 will be assessed at baseline and at completion of idronoxil therapy per cycle. Biomarker and plasma idronoxil levels to be correlated with anti-cancer activity and any toxicity.

Statistical Methods
	
Statistical analyses will be primarily descriptive in nature and statistical hypothesis testing will not be performed. All patients will be included in the evaluation of safety. Data will be presented by Cohort, by idronoxil and carboplatin dosages, and by tumour type.

Inclusion Criteria
	
 
1. Provision of informed consent.
 
2. Male or female <math>\geq 18</math> years of age.
 

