## 6 STUDY OBJECTIVES

### 6.1 PRIMARY OBJECTIVES

- to determine the tolerability, adverse event profile, maximum tolerated dose (MTD), and dose-limiting toxicities (DLTs) of idronoxil in a suppository dosage form (NOX66) in patients with refractory solid tumours, both as a single agent and in combination with carboplatin
- to determine if idronoxil in a suppository dosage form (NOX66) is able to combine with a standard dosage of carboplatin to produce a meaningful anti-cancer effect in solid tumours considered to be refractory to cytotoxic chemotherapy
- to determine if idronoxil in a suppository dosage form (NOX66) is able to combine with dosage of carboplatin two-thirds of the standard dosage to produce a meaningful anti-cancer effect in solid tumours considered to be refractory to cytotoxic chemotherapy.

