### 13.2 STATISTICAL METHODOLOGY

This section describes the planned statistical analyses in general terms. A complete description of the statistical analysis will be specified in a statistical Analysis Plan (SAP) finalised prior to completion of the study.

The primary objectives of this study are to determine

- (a) the tolerability, adverse event profile and any dose limiting toxicities (DLTs) of idronoxil (as NOX66) in combination with carboplatin in patients with refractory solid tumors, and
- (b) the ability of idronoxil (as NOX66) in combination with carboplatin to deliver a meaningful anti-cancer effect in refractory tumours considered unlikely to respond to carboplatin.

Secondary objectives are:

- 1) to characterize the pharmacokinetic profile of idronoxil administered rectally as NOX66, and
- 2) to determine any correlation between biomarkers of idronoxil biological activity and any clinical anti-tumor activity or toxicity observed in patients treated with NOX66.

These objectives are to be addressed in the context of an open-label, dose-escalation study; therefore, statistical hypothesis-testing will not be performed, and analyses will be primarily descriptive in nature.

All patients will be included in the safety evaluation. Data will be presented by dose cohort. Data from Study NOX66-001A will be used to guide dosing for future Phase II trials.

**Populations for Analysis:** There will be three study populations defined for this study.

The safety population will consist of all patients who received at least one dose of idronoxil. This population will be used in all safety summaries.

The efficacy population will consist of all patients with measurable or evaluable disease at baseline who complete at least 1 cycle of treatment and undergo at least one follow-up tumor

evaluation.

The pharmacokinetic/biomarker population will be a subset of the safety and efficacy populations and consist of all patients who have sufficient idronoxil plasma data for analysis. All such patients will be evaluated unless significant protocol deviations have impacted the data. Changes to the procedures, which may impact the quality of pharmacokinetic data, will be considered significant protocol deviations. Examples include sample processing errors that lead to inaccurate bio- analytical results and/or inaccurate dosing on the day of pharmacokinetic sampling.

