ECG parameters at each time point will be presented by patient and by time point. The results will be presented by dose cohort.

**Efficacy Analysis:** Tumor measurements will be assessed by radiologic methods at baseline and at subsequent intervals at the discretion of the Investigator but not greater than every 12 weeks. Efficacy variables will include overall response, duration of objective response, time to progression, progression free survival (PFS), and overall survival. Response and progression will be assessed according to RECIST (Eisenhauer et al., 2009).

Continuous data will be summarized by descriptive statistics, including sample size, mean, standard deviation, median and range. Categorical data will be summarized by the number and percentage of patients. For the time-to-event endpoints, Kaplan-Meier estimates will be plotted.

Median event time and the associated 95% confidence interval will be provided. In addition, all the data will be presented in the data listings. The final statistical analysis for the study will be scheduled when all patients have completed at least one course of study drug administration, have reached a study endpoint (e.g., DLT or disease progression), and have at least 28 days of follow-up.

Best overall response, duration of objective response (complete response or partial response), PFS, time to progression and overall survival will be listed for all patients with measurable or evaluable disease by dose level. Any patient with insufficient data to determine response will be classified as a non-responder. Among patients with an objective response, duration of objective response will be defined as the time from the initial CR or PR to the time of disease progression or death on study, whichever occurs first. For patients who are alive and have not experienced disease progression on study, duration of objective response will be censored at the day of the last tumor assessment. Time to disease progression is defined as the time from the first day of study drug administration (Day 1) to disease recurrence or progression on study. Progression free survival (PFS) is defined as the time from the first day of study drug administration (Day 1) to disease recurrence or progression, or death on study. Patients who are alive and disease progression-free will be censored at the date of last disease evaluation.

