The primary aim of this phase is to investigate if NOX66 can induce a meaningful clinical response (complete or partial remission by RECIST criteria) in combination with carboplatin in cancers that have stopped responding to standard chemotherapy and generally would be considered unlikely to respond to further standard therapy. Furthermore, it will be investigated if a meaningful anti-cancer effect is possible combined with a dosage of carboplatin that would otherwise be regarded generally as well tolerated but unlikely to deliver a significant anti-cancer effect.

The **Phase IIa Arm** can commence providing that a meaningful clinical response (partial or complete tumour response as determined by RECIST criteria) has occurred in some patients in the Phase Ib Arm. Up to a maximum of 12 patients can be recruited of similar tumour type and disease status as the Phase Ib patients showing the clinical response and form the basis of 2 new patient cohorts.

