2.3 Study objectives

The primary objectives of this study are:

- to determine the tolerability, adverse event profile, maximum tolerated dose (MTD), and dose-limiting toxicities (DLTs) of NOX66 in a suppository dosage form in patients with refractory solid tumours, both as a single agent and in combination with carboplatin
- to determine if NOX66 in a suppository dosage form is able to combine with a standard dosage of carboplatin to produce a meaningful anti-cancer effect in solid tumours considered to be refractory to cytotoxic chemotherapy
- to determine if NOX66 in a suppository dosage form (NOX66) is able to combine with a dosage of carboplatin two-thirds of the standard dosage to produce a meaningful anti-cancer effect in solid tumours considered to be refractory to cytotoxic chemotherapy.

The secondary objectives are:

- to characterise some key pharmacokinetic features of NOX66 when administered rectally
- to determine if various biomarkers of NOX66 biologic activity have any correlation to the efficacy or toxicity of NOX66 in combination with carboplatin.

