7.1 Efficacy

Tumour measurements will be assessed by radiological methods. Longest dimensions for each target lesion within each patient will be summed at each measurement time. Sums will be analysed by descriptive statistics by cohort for each measurement time within each phase of the study.

Response to treatment, as measured by the RECIST criteria, as well as duration of response will be assessed following each radiological assessment. The best overall response and the duration of that response will be summarised and tabulated by cohort. Duration of the objective response will be defined as the time from the initial CR or PR to the time of disease progression or death on study, whichever occurs first.

For patients who are alive and have not experienced disease progression on study, duration of objective response will be censored at the day of the last tumour assessment. Time to disease progression is defined as the time from the first day of study drug administration (Day 1) to disease recurrence or progression on study. Progression free survival (PFS) is defined as the time from the first day of study drug administration (Day 1) to disease recurrence or progression, or death on study. Patients who are alive and disease progression-free will be censored at the date of last disease evaluation. Progression-free survival and overall survival will be analysed using the Kaplan-Meier actuarial method. Median times and 95% confidence intervals will be computed by cohort.

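### Response is tabulated by NOX66 cohort only, so the planned table cannot show whether two-thirds-dose carboplatin produced any response, which is what the third primary objective asks

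*SAP*

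**What the plan says.** **Objectives.** Protocol 6.1 lists an objective for standard-dose carboplatin and, separately, "to determine if idronoxil in a suppository dosage form (NOX66) is able to combine with dosage of carboplatin two-thirds of the standard dosage". SAP 2.3 repeats the pair, the second asking whether NOX66 "is able to combine with a dosage of carboplatin two-thirds of the standard dosage to produce a meaningful anti-cancer effect". SAP 2.2 raises the reduced-dose question again: "Furthermore, it will be investigated if a meaningful anti-cancer effect is possible combined with a dosage of carboplatin", meaning one otherwise thought too low to have much effect.

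**Treatment.** Under Protocol 7.1 and 10.1.2 and SAP 2.2, each Phase Ib patient starts at AUC 4 for three 28-day cycles and then moves to AUC 6 for up to three more. The Protocol makes this conditional on no dose-limiting toxicity and no progression.

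**Response analysis.** SAP 7.1: "The best overall response and the duration of that response will be summarised and tabulated by cohort". SAP 3.3 labels the cohorts 400 mg and 800 mg, which are NOX66 doses. The response table and figure listed in SAP 11 carry no carboplatin stratum.

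**Presentation elsewhere.** The Protocol synopsis states: "Data will be presented by Cohort, by idronoxil and carboplatin dosages, and by tumour type". Protocol 13.1 expresses its minimum of eight patients per combination. Protocol 13.2 folds the two efficacy objectives into one, "the ability of idronoxil (as NOX66) in combination with carboplatin to deliver a meaningful anti-cancer effect in refractory tumours", and then says "Data will be presented by dose cohort" and that best response and the time-to-event outcomes "will be listed for all patients with measurable or evaluable disease by dose level". SAP 8.2 tabulates adverse events separately for monotherapy, AUC 4 and AUC 6.

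**The concern.** Best overall response is one value per patient over the whole study. When every patient is due to pass through both carboplatin doses, a count by NOX66 cohort adds together the two situations that the objectives keep apart. Once a cohort has a responder and at least one patient has reached AUC 6, the planned table cannot say whether the lower carboplatin dose gave any response.

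No rule assigns a response to a carboplatin dose, and no denominator is set for each dose. Any split made later from the listings would be chosen with the results in view, in an open-label study where scan timing is largely at the Investigator's discretion.

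**Working it through.** **1. Which doses the objectives mean.** AUC 4 / AUC 6 = 0.667, and the dose caps in Protocol 10.1.2 give 600 mg / 900 mg = 0.667. I therefore read two-thirds of standard as AUC 4 and standard as AUC 6. This is an inference; the documents do not state it outright. SAP 8.2 calls AUC 4 low and AUC 6 high.

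**2. The plan's own size.** Two cohorts × 8 = 16, as stated. Protocol 10.1.3 counts four NOX66/carboplatin combinations, and 4 × 8 = 32. Sixteen patients give eight per combination only if each counts under both carboplatin doses and all reach Cycle 4. Retention to Cycle 4 is not given. If it were 50% to 90% (assumption), the expected number reaching AUC 6 per cohort would be 8 × 0.5 = 4.0 to 8 × 0.9 = 7.2.

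**3. What the planned row shows.** Illustration, not from the documents: 8 evaluable patients, 2 responders, exact (Clopper-Pearson) 95% intervals.

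| First seen under AUC 4 | First seen after AUC 6 | Planned cohort row | AUC 4 result |
|---|---|---|---|
| 0 | 2 | 2/8, 25% (3.2–65.1%) | 0/8, 0% (0–36.9%) |
| 1 | 1 | 2/8, 25% (3.2–65.1%) | 1/8, 12.5% (0.3–52.7%) |
| 2 | 0 | 2/8, 25% (3.2–65.1%) | 2/8, 25% (3.2–65.1%) |

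The third column does not change.

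**4. Whether another output fills the gap.** Lesion sums are planned by cohort, measurement time and phase, but both carboplatin doses fall within Phase Ib. The response figure is by cohort. The Overall column pools further. The exploratory factors in SAP 7.3 do not include carboplatin dose.

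**5. Whether dates could separate the doses.** Carboplatin is due on Day 2 of each 28-day cycle, so cycle k falls on Phase Ib Day 28(k − 1) + 2: Days 2, 30, 58 (AUC 4) and 86, 114, 142 (AUC 6). Phase Ib Day 1 comes 21 days after Phase Ia Day 1. Protocol 10.3.1 and 13.2 set 12 weeks (84 days) as the longest scan interval but do not say when it starts. On planned dates at that interval:

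| Clock starts at | First scan (Phase Ib day) | Second scan | Scan between Days 58 and 86? |
|---|---|---|---|
| First NOX66 dose | 84 − 21 + 1 = 64 | 148 | Yes |
| Phase Ib Day 1 | 84 + 1 = 85 | 169 | Yes, by one day |
| Baseline imaging, d days before Phase Ia Day 1 (d = 0–28) | 64 − d | 148 − d | d = 0–5 yes (Days 59–64); d = 6 falls on Day 58; d = 7–28 no (Days 36–57) |

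For d = 7–28 the second scan falls on Days 120–141. The interval before it contains one AUC 4 dose (Day 58) and two AUC 6 doses (Days 86 and 114), so a response first seen there cannot be assigned to either dose.

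**The case against.** **The study is descriptive and small.** Protocol 13.2 rules out hypothesis testing and SAP 7 disclaims powered efficacy objectives. With 16 patients and full listings, response and dosing dates can be read case by case, and patients who stop before Cycle 4 have only AUC 4 responses. This limits the consequence but does not remove the gap. A descriptive primary objective still needs a descriptive output, and listings supply dates but no rule or denominator.

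**AUC 6 can never be isolated.** It always follows AUC 4 and is reached only by selected patients. That stands, and it limits what any table can say about the standard-dose objective. It does not affect a count of responses documented before the first AUC 6 dose.

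**Readings that go too far.**
- A reader might infer that the Protocol contradicts itself. Presentation by dose cohort in 13.2 is less specific than the synopsis and does not exclude it. Dose level is not defined, and Protocol 9.3 and 10.1.2 use the term for combination therapy. The wording needs aligning.
- A reader might count 22 of the 29 possible values of d as unassignable and conclude that most responses would be lost. That requires a clock running from baseline imaging and scans at the longest permitted interval. The other two clocks separate the doses, Protocol 10.3.1 asks for baseline imaging close to treatment start, and offsets are not frequencies.

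**Conclusion.** The point holds. Followed exactly, the SAP produces no output for the primary objective on two-thirds-dose carboplatin, unless a cohort has no responders or none of its patients reaches AUC 6. In the illustration, an AUC 4 response proportion anywhere from 0/8 to 2/8 sits behind the same 2/8.

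This rests on reading AUC 4 and AUC 6 as the two doses in the objectives, and on the planned sequence being followed. Scan timing is a range of possible cases: two of the three candidate clocks separate the doses on planned dates, and the third does so only when baseline imaging is close to first dosing.

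A reader might also infer that the Phase IIa decision depends on this table. The documents leave that choice to agreement between the Principal Investigators and the Sponsor and do not tie it to any table. No error rate or power figure is touched. The dose-limiting toxicity summary promised in Protocol 13.2 but absent from the SAP table list, and the passages on the toxicity window that must be reconciled (Protocol 10.1.4 against 7.1 and 10.1.2), are separate matters and lend this point no weight.

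**What to change.** 1. **Align the wording.** Bring Protocol 13.2 and SAP 7.1 into line with the synopsis on presentation by carboplatin dosage.

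2. **Add one Phase Ib response table to SAP 7.1 and SAP 11**, by NOX66 cohort and carboplatin period, using the date CR or PR is first documented. Response stays measured against study baseline. The rows are mutually exclusive:
   - (i) First documented before the first AUC 6 dose. N = efficacy population, including patients who never reach AUC 6.
   - (ii) First documented after the first AUC 6 dose, in patients with a scan showing no response between the last AUC 4 and first AUC 6 doses. N = efficacy-population patients who received AUC 6, had such a scan and were not already in response. Label it *AUC 6 after AUC 4* and state that it does not estimate AUC 6 alone.
   - (iii) Not assignable: first documented after the first AUC 6 dose, with no scan between those two doses.

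   A response and its duration stay in the row of first documentation even if it is confirmed, or deepens from PR to CR, after the switch; a footnote counts such cases. Say how a scan on a dosing day is counted. Flag patients whose carboplatin was reduced or withheld by the dose actually received. Report any Phase IIa cohort separately under its own combination.

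3. **State when the 12-week imaging clock starts.** No extra scan is required; row (iii) shows whatever is lost.

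**Cost.** One table, one rule and a few aligned sentences, with no new data. Denominators will be small and intervals wide: one response among four patients, for example, is 25% (exact 95% interval 0.6–80.6%). The standard-dose objective is answered only for AUC 6 given after AUC 4.

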7.2 Pharmacokinetics

Plasma and 24-hour urine levels of NOX66 and NOX66 metabolites (idronoxil glucuronide, idronoxil sulphate) will be measured. Pharmacokinetic parameters will minimally include C_{max} , T_{max} , AUC_{0-24h} , $AUC_{0-\infty}$, and $t_{1/2}$ and be calculated using standard analysis. Descriptive results will be presented for the pharmacokinetic parameters by dose cohort.

In the event that PK concentrations are not detectable at the time points necessary and a meaningful PK curve (i.e. concentration vs time) cannot be estimated, descriptive statistics will be used to summarize PK concentration.

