**Table 5. Schedule of Assessments -Phase Ia (Run-In) Arm**

Study Day	1	8	15	21
Physical Examination (PE)	X	X	X	
12 Lead ECG 	X	X	X	
Vital Signs 	X	X	X	
Clinical laboratory tests				
Complete Blood Count (CBC) 	X	X	X	
Serum chemistry 	X	X	X	
Urinalysis (dipstick) 	X	X	X	
Concomitant medication review	X	X	X	X
PK /Biomarker sampling	X 	X 	X 	
Urine collection 	X	X	X	
Adverse events/toxicity assessment	X	X	X	X
Dispense study drug	X		X	

 ECG conducted 1-hour post NOX66 dosing on Days 1 and 8; any time Day 15.

 Vital signs = blood pressure, pulse, respiratory rate and body temperature.

 See Section 6.4 for list of blood tests.

 Plasma for PK analysis to be collected (Day 1) at t = 0, 30 min, 1 hr and 2 hr post-dosing.

 Plasma for PK analysis to be collected (Day 8) at t = 0, 1 hr and 2 hr post-dosing.

 Plasma for PK analysis to be collected (Day 15) at 24 hr post-dosing.

 24-hr urine sample to be collected starting from the time of NOX66 dosing on Day 1.

 Return study drug for in-clinic administration

 Phone call to confirm dose level and continuation to Phase1b.

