**Table 10. PK Blood Sampling Schedule for Phase Ia (Run-In) Arm**

Day	Sampling time in relation to NOX66 administration
1	t = 0 (pre-dose), then 0.5, 1, and 2 hr post-dose*
8	t = 0 (pre-dose), then 1 hr and 2 hr post-dose*
15	t = 24 hr post-dose

\*Post dosing sampling may be taken following administration of the first suppository for Cohort 2 patients.

24-hour urine will be collected on Days 1, 8 and 15, commencing from the time of NOX66 administration on those days and returned at following visit day.

**Phase Ib (Combination) Arm:** Blood samples to be collected from all patients on Day 7 of each Treatment Cycle at t = 1hour post-dosing. Post dosing sampling may be taken following administration of the first suppository for Cohort 2 patients.

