**Pharmacokinetics:** Plasma and 24-hour urine levels of idronoxil and idronoxil metabolites (idronoxil glucuronide, idronoxil sulphate) will be measured. Pharmacokinetic parameters will minimally include  $C_{max}$ ,  $T_{max}$ ,  $AUC_{0-24hr}$ ,  $AUC_{0-\infty}$ , and  $t_{1/2}$  and be calculated using standard analysis. Descriptive results will be presented for the pharmacokinetic parameters by dose cohort.

In the event that PK concentrations are not detectable at the time points necessary and a meaningful PK curve (i.e. concentration vs time) cannot be estimated, descriptive statistics will be used to summarize PK concentration.

**Concomitant medications:** Concomitant medications will be listed by dose cohort for all patients.

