3.1 Analysis populations

There will be three study populations defined for this study.

The safety population will consist of all patients who received at least one dose of NOX66. This population will be used in all safety summaries.

The efficacy population will consist of all patients with measurable or evaluable disease at baseline who complete at least 1 cycle of combination treatment and undergo at least one follow-up tumour evaluation.

The pharmacokinetic/biomarker population will be a subset of the safety and efficacy populations and consist of all patients who have sufficient NOX66 plasma data or biomarker plasma data for analysis. All such patients will be evaluated unless significant protocol deviations have impacted the data. Changes to the procedures, which may impact the quality of pharmacokinetic data, will be considered significant protocol deviations. Examples include sample processing errors that lead to inaccurate bio-analytical results and/or inaccurate dosing on the day of pharmacokinetic sampling.

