3.2 Visit windows

The Screening visit must be at least 7 days prior to the first dose of NOX66.

All other visits should be within ± 1 day of the planned study visit. All visits will be analysed based on the planned visit, as opposed to when the visit actually occurred.

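### AUC0-24h, AUC0-infinity and half-life are required outputs, but no plasma is drawn between 2 h after a dose and the end of the dosing interval, and no rule says how to bridge the gap

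*SAP*

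**What the plan says.** **Required outputs.** SAP 7.2 and Protocol 13.2 carry the same list. "Pharmacokinetic parameters will minimally include" is followed by Cmax, Tmax, AUC0-24h, AUC0-infinity and half-life, summarised by dose cohort. The method is given only as standard analysis. SAP section 11 plans a table of PK coefficients.

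**Plasma schedule.**
- Day 1 (Protocol Table 10): "t = 0 (pre-dose), then 0.5, 1, and 2 hr post-dose".
- Day 8 (Table 10): "t = 0 (pre-dose), then 1 hr and 2 hr post-dose".
- Day 15 (Table 5 footnote, same time in Table 10): "Plasma for PK analysis to be collected (Day 15) at 24 hr post-dosing". Run-in dosing ends on Day 14.
- Phase Ib (Protocol 10.4.6): "Blood samples to be collected from all patients on Day 7 of each Treatment Cycle at t = 1hour post-dosing".

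**Dosing interval** (Protocol Table 2): 24 h in Cohort 1 and 12 h in Cohort 2.

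**Fallback.** Both documents fall back to descriptive statistics on concentrations. The condition opens "In the event that PK concentrations are not detectable at the time points necessary" and adds that a meaningful curve cannot be estimated.

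**Timing.** SAP 3.2 says "All visits will be analysed based on the planned visit, as opposed to when the visit actually occurred". SAP 3.1 says "Changes to the procedures, which may impact the quality of pharmacokinetic data, will be considered significant protocol deviations". Protocol Appendix B has the time of draw written on every tube.

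**The concern.** AUC0-24h needs the concentration curve over the whole day. AUC0-infinity and half-life need a terminal slope. The schedule observes the first 2 h after a dose and then nothing until the end of the interval.

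Neither document says which day's dose the AUC refers to, whether days may be combined, how the 2 h value is joined to the end of the interval, or how the terminal slope is fitted. In Cohort 2 a second dose also falls inside the 0-24 h window, with no rule for it.

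An analyst who follows the list would have to choose these rules after seeing the data, and the choice drives the exposure values. PK is a secondary objective and no decision within the study uses it. However, Protocol 13.2 says the study's data will guide dosing in later Phase II trials, so the reported values may be used.

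**Working it through.** The documents give no figure to reproduce, so the check starts from the schedule and then uses an illustrative model.

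**1. Coverage (schedule only).** Samples strictly between 2 h and the end of the interval: none on Day 1, Day 8, Day 15 or the Phase Ib days.
- Cohort 1: (24 − 2)/24 = 22/24 = 92% of the interval unsampled.
- Cohort 2: (12 − 2)/12 = 10/12 = 83% unsampled.

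**2. Points for a terminal slope (schedule only).** Day 1 has two samples after the peak if the observed peak is at 0.5 h, one if at 1 h and none if at 2 h. Day 8 gives no more. No day has three points after the peak.

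**3. Assumed model.** The documents give no half-life or absorption rate. I assume one compartment with first-order absorption and dose/volume = 1, half-life 1, 2, 4 or 8 h and ka 1, 2 or 4 per h (12 scenarios), with ke = ln 2 / half-life.
- Single dose: C(t) = ka/(ka − ke) × [exp(−ke·t) − exp(−ka·t)].
- Steady state, interval τ: C(t) = ka/(ka − ke) × [exp(−ke·t)/(1 − exp(−ke·τ)) − exp(−ka·t)/(1 − exp(−ka·τ))].
- True AUC, single dose to infinity or steady state over τ: 1/ke.

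**4. Single-day profile.** Share of AUC0-infinity after the last Day 1 sample = [ka·exp(−2ke) − ke·exp(−2ka)]/(ka − ke).
- Half-life 1 h, ka 4: (4 × 0.25 − 0.6931 × 0.000335)/3.3069 = 0.30.
- Half-life 8 h, ka 1: (0.8409 − 0.0866 × 0.1353)/0.9134 = 0.91.
- Range over the grid: 30-91%. At half-life 0.5 h: 10-32%.

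**5. Day 8 composite.** Points are 0, 1 and 2 h, plus τ with the pre-dose value reused. Worked case, Cohort 1, half-life 4 h, ka 2: C = 0.0174, 0.7871, 0.7664, 0.0174; truth 1/ke = 5.771.
- Linear: 0.402 + 0.777 + 22 × (0.7664 + 0.0174)/2 = 0.402 + 0.777 + 8.622 = 9.80, or 1.70 times truth.
- Log-down: 0.402 + 0.777 + 22 × (0.7664 − 0.0174)/ln(0.7664/0.0174) = 0.402 + 0.777 + 4.352 = 5.53, or 0.96 times truth.

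| Day 8 composite, multiple of truth | Cohort 1 | Cohort 2 |
|---|---|---|
| Interval AUC, linear join | 1.12-3.28 | 0.99-1.74 |
| Interval AUC, linear-up/log-down | 0.80-0.98 | 0.80-0.98 |
| Half-life from the 2 h and τ values | 1.00-1.09 | 1.00-1.15 |

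**6. Slower absorption.** With ka 0.5 per h and the same half-lives, log-down gives a Cohort 1 AUC of 0.71-0.81 times truth. Half-life reads 1.21-1.54 (Cohort 1) and 1.48-1.75 (Cohort 2) times truth, because the slope then partly reflects absorption.

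**7. Measurable trough.** The composite needs a quantifiable pre-dose value. At half-life 1-2 h that value is 0.00002-0.07% of the 2 h value in Cohort 1 and 0.1-4% in Cohort 2. At 4-8 h it is 2-17% and 18-47%. No assay limit is given.

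**8. What the schedule does support.** On the grid, Day 1 trapezoidal AUC0-2h is 0.93-0.97 of truth and the highest Day 1 value is 0.97-1.00 of the true peak. The true peak falls after 2 h in 2 of 12 scenarios (latest 2.7 h). The three-point Day 8 AUC0-2h is 0.73-0.97 of truth.

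**The case against.** **The fallback already protects the report.** This stands in part. It shows that an analyst is not forced to report parameters that cannot be estimated, and with a very short half-life it would probably apply. Its trigger, however, is concentrations too low to detect. Detectable concentrations at too few times do not clearly meet it.

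**A Day 8 composite solves the problem.** A reader might infer that using the pre-dose value as the end-of-interval value recovers AUC and half-life. It does so reasonably on the grid in step 5, but not with slower absorption (step 6) and not without a measurable trough (step 7). Neither document specifies the composite. Protocol 5.5 describes rectal absorption as generally fast but gives no rate for this product.

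**Dose proportionality would be misread.** With a linear join, a true Cohort 2 to Cohort 1 exposure ratio of 2.0 would read as 1.05-1.77 on the grid. That needs a composite, a linear join over 22 h and a between-cohort comparison. The documents state none of these and have no dose-proportionality objective. With log-down the same ratio reads 2.00-2.08 on the grid. The figure shows sensitivity to the rule; it is not a consequence of the plan as written.

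**SAP 3.2 makes PK use nominal times.** That reading is strained. The section concerns visit days, and draw times are recorded. What remains is that no text says PK uses actual times.

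**Conclusion.** The point holds. Three required outputs cannot be supported by the sampling schedule on any single day unless elimination is very fast, and no composite rule is stated. The uncovered 22 of 24 h and 10 of 12 h follow from the schedule alone and need no model.

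The size of the effect rests on assumed PK values. Within that model, two ordinary joining rules applied to the same Cohort 1 data give an AUC anywhere from 0.80 to 3.28 times truth. The log-down figures are not a general bound, since slower absorption widens them.

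The consequence is confined to the PK section of the report and to any later dosing guidance drawn from it. Safety conclusions, escalation and the primary objectives are untouched. It should be corrected before the PK analysis, but it does not threaten the study.

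**What to change.** In SAP 7.2 and Protocol 13.2:

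1. Remove AUC0-24h, AUC0-infinity and half-life from the required minimum.
2. Require what the schedule supports: Day 1 AUC0-2h, the highest observed concentration and its time within 0-2 h, and the concentration at each scheduled time, including the Day 8 pre-dose and Day 15 values. If Day 8 is compared with Day 1, use the common times 0, 1 and 2 h and note that the three-point Day 8 AUC0-2h can read low.
3. If a steady-state interval AUC or apparent half-life is reported at all, label it exploratory and limit it to patients with a quantifiable Day 8 pre-dose value. State the linear-up/log-down rule and the steady-state and one-compartment assumptions, give the number of patients per cohort, and warn that with slow absorption the slope may reflect absorption.
4. Extend the fallback to detectable concentrations at too few time points.
5. State that PK calculations use actual time since the last dose, and say which outputs apply to the glucuronide and sulphate metabolites.

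**Cost.** Wording only, with no added draws or visits. Draw times are already on the tubes. The time of the last suppository before the Day 8 and Day 15 draws needs one CRF field if it is not already collected. The price is that the report no longer promises AUC0-24h, AUC0-infinity or half-life.

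**Separate points to reconcile:** the Day 15 urine start in Protocol 10.4.6 against the rest period in Table 7 and the Table 5 urine footnote; which Day 14 dose the Cohort 2 Day 15 sample is timed from; and the broader wording of the PK objective in Protocol 13.2 against 6.2.
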